The clinical presentation of scabies has been previously described in other tropical regions. A recent study conducted in Yaoundé showed lesions were most commonly present in the infragluteal folds, on the wrists and in the intergluteal folds. Types of lesions were also documented, with crusty lesions being the most common type(8).

For persons never before affected by scabies it can take up to 6 weeks for symptoms to begin, while the mites can already be spread during this asymptomatic period. However in reinfestation symptoms usually occur much earlier(1-4 days)(9).

There exist different agents for the treatment of Scabies with comparable efficacy(10–12). Ivermectin seems to be most effective for large populations with high prevalence of scabies(10). However the use of ivermectin can lead to serious adverse events in patients with high concentration of *Loa Loa* microfilariae in the blood(13). Since *Loa Loa* is endemic in Gabon(14), treatment with ivermectin for Scabies should only be given if high *Loa* parasitemia can be excluded. Furthermore, only limited safety data exists for children under 5 years of age or weighing less than 15 kg, a group in which scabies is common(9).

Permethrin is the first line topical treatment for Scabies, however it comes at a higher cost per treatment, and is more difficult to obtain in Gabon than Benzyl Benzoate, a substance which also offers good efficacy and safety(10–12).

It is recommended that the contact persons of an affected individual shall also be treated at the same time, to ensure long term success of treatment, prevent reinfestation and infestation of contact persons(9,10,15). However this recommendation lacks a solid background of evidence. A recent review concluded that the effects of treating contact persons to prevent new infestation are unknown(16).

There is currently an outbreak of itching lesions suggestive of scabies in Gabon that the local population has named “gratti gratta” but there has been so far no raised attention from the local medical scientific community to describe these lesions and definitely attribute the diagnosis of scabies and sensitize the population in measure for the control of the epidemic.

Research question

We propose a randomized controlled trial comparing treatment of only affected persons presenting at our medical research center (which we will call individual treatment) to treatment of the entire household (which we will call household treatment), with both groups using the same treatment regimen with benzyl benzoate. We hereby aim to assess the practice of systematically recommending household treatment and if it provides a benefit for the index case by preventing reinfestation.

We will also assess the number of household members affected 4 weeks after treatment, by examining all household members that are present on the day of the visit. Since the presence of itching and skin lesions in a household with a diagnosed scabies case is known to be highly specific (15,17), we will also assess the number of probable scabies cases per household before and after treatment according to the judgment of the household responsible person. Cases identified this way will be defined as “probable” and cases identified through clinical diagnosis by a physician will be defined as “confirmed”.

We will further assess clinical characteristics of Scabies and demographic factors associated with its appearance in Lambaréné, Gabon, and surroundings. Although similar studies have been conducted elsewhere, little is known about Scabies in Gabon. A better understanding of the demographic profile of persons affected by the disease can benefit future control of the disease.

Study Objectives (Aims)

Primary objectives

To compare the effectiveness of individual vs household treatment for persons affected by scabies.

Secondary objectives

To compare the effectiveness of individual vs household treatment in terms of proportion of household members affected after 4 weeks.

To describe the clinical presentation of scabies and demographic profiles of persons affected presenting at our medical research center in Lambaréné, Gabon.

To assess the tolerability and safety of benzyl benzoate.

Endpoints

Primary Endpoint

The primary efficacy outcome will be clinical cure after 4 weeks.

Secondary Endpoint

Secondary endpoints will include the rate of probable and confirmed scabies cases per household after 4 weeks.

Methods and Materials

Study Population

The study will be conducted at the Centre de Recherches Médicales de Lambaréné (CERMEL). Cases will be identified from patients presenting at the medical research center, which are mostly patients from screening activities conducted for malaria trials. All household members that present at the medical research center from a household with at least one case of scabies will be included. The first affected subject included of a household will be defined as the index case.

Sample size

Estimating a cure rate of 70% and 95% for individual vs. family treatment respectively we calculated a sample size of 35 affected subjects per group to provide a power of 80% with an alpha of 0,05.

When estimating that on average one additional household member affected will present at the medical research center alongside an index case, we will aim to include at least 35 different households.

Scabies Diagnosis and Data Collection

Subjects will be checked for lesions typical of scabies by a physician. The diagnosis of scabies will be made by clinical examination, a method of diagnosis which has been used in a number of other studies to diagnose scabies and has been shown to be highly sensitive and specific. Scabies will be defined as the presence of itching together with typical distribution of lesions, such as on the hands, wrists, elbows, axillae, knees, buttocks, genitalia in men, breast areolae in women, palms and soles in children under the age of two(18,19).

The lesions will be described in terms of location and spread on the body, itching and superinfection. A severity scale will be used classifying the cases into mild, moderate, severe and crusted according to the number of lesions counted. Photos of characteristic lesions and lesions of special interest will be taken. In case of lesions of unclear origin images will be assessed via a telemedical consultation by a dermatologist at the department of tropical medicine, Bernhard Nocht Institute of Tropical Medicine, Hamburg, Germany and a recommendation on treatment will be given. Images will be sent pseudonymized to protect subject privacy.

In the course of this study we will assess the use of a low-cost videomicroscope for the diagnosis of scabies, a method which has previously shown promise as a cost-effective way to definitely attribute lesions to scabies infestation(20). Thus, all patients will be examined with such a videomicroscope.

Demographic data including age, sex and household size will be assessed.

Study treatment and follow up

For the treatment part of this study index cases will be randomized in either of two groups and subjects of the respective household will follow the randomization outcome of the index case. Randomization will be done in RedCAP. In the first group only subjects affected by scabies shall be treated. In the second group all persons living in the same household as the index case shall be treated, and treatment will be dispensed according to the number of household members stated by the household responsible person. For both groups the choice of treatment will be a single application of benzyl benzoate 25%, which shall be mixed with an equal quantity of water for older children and with 3 parts of water for infants. Subjects will be instructed on the use of the treatment and given a standardized leaflet with instructions, however the use of the treatment will not be supervised, making this an intervention conducted in a real world setting.

Subjects will be followed up after 4 weeks. At follow up visits the subjects will be questioned about the symptoms of scabies and any adverse events experienced and examined by a physician. Cure will be defined as the clinical improvement in lesions with no new lesions. All household members present at this visit will also be examined for scabies. Subjects and household members considered not cured or newly infested will be treated.

Safety

Benzyl Benzoate is generally safe to use for all persons, including infants and pregnant women. It is contraindicated only for persons with known hypersensitivity to benzyl benzoate, which will constitute an exclusion criterium. Adverse events include skin irritation and stinging sensation(21). In case of accidental ingestion subjects are requested to contact the principal investigator.

Ethical Considerations

To maintain randomization into the individual and household treatment groups and to avoid preferential withdrawal, loss to follow up, or spillover effects the informed consent process will be performed in a two step approach.

First all participants and/or parents/guardians (as applicable) shall be informed about all aspects of this clinical trial including the study medication. However, the respective intervention strategies (individual versus household treatment) will not be disclosed to the participants in the first step of the informed consent process. After randomization, only for the household treatment group, a person responsible for the household shall be informed about and agree to the treatment of the entire household.

The study will be conducted according to the ethical principles stated in the Declaration of Helsinki, the applicable guidelines for ICH-GCP, and the applicable laws and regulations of Gabon. Approval from the CERMEL ethics review committee will be acquired. The study will be conducted in compliance with the study protocol.

Data

Data will be collected electronically in RedCAP using the online interface and the RedCAP mobile app for offline data collection.

Funding

The trial will be institutionally funded by the Department of Clinical Research, CERMEL and the Bernhard Nocht Institute.

Bibliography

2. Fuller LC. Epidemiology of scabies. *Curr Opin Infect Dis.* 2013 Apr;26(2):123–6.
6. Burkhart CG. Scabies: An Epidemiologic Reassessment. *Ann Intern Med.* 1983 Apr 1;98(4):498.
7. Hadfield-Law L. Scratching the itch: management of scabies in A&E. *Accid Emerg Nurs.* 2000 Oct;8(4):230–2.
9. CDC - Scabies [Internet]. [cited 2018 May 22]. Available from: <https://www.cdc.gov/parasites/scabies/index.html>

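### The week-4 household endpoint measures the whole strategy, but it ignores the baseline case count already collected and cannot show whether treating unaffected contacts prevents new infestation

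*Combined protocol and SAP*

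**What the plan says.** The secondary objective (Study Objectives) compares "individual vs household treatment in terms of proportion of household members affected after 4 weeks". The Secondary Endpoint follows it: "Secondary endpoints will include the rate of probable and confirmed scabies cases per household after 4 weeks". Neither limits the count to members free of scabies at baseline or adjusts for those who were not.

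The documents describe who is treated in four places:

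- Research question: the trial is introduced as "comparing treatment of only affected persons presenting at our medical research center (which we will call individual treatment").
- Study Population: "All household members that present at the medical research center from a household with at least one case of scabies will be included".
- Study treatment and follow up, individual arm: "In the first group only subjects affected by scabies shall be treated".
- Study treatment and follow up, household arm: "In the second group all persons living in the same household as the index case shall be treated".

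On baseline information, the Research question section says "we will also assess the number of probable scabies cases per household before and after treatment", as judged by the person responsible for the household. Household size is among the demographic data (Scabies Diagnosis and Data Collection). No analytic use of the pre-treatment count is stated. Members who do not come to the centre have no planned baseline examination.

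The background text before the Research question cites a review which concluded that "the effects of treating contact persons to prevent new infestation are unknown". It also says that first-time symptoms may take up to 6 weeks to appear.

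**The concern.** Read together, the Research question and Study Population sections mean that an affected member who stays at home is not treated in the individual arm. In the household arm the same person is given treatment. The arms therefore differ in two ways: existing cases at home are treated, and unaffected contacts are treated. The week-4 proportion adds the two effects together.

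Two things are at stake. First, the gap in evidence that the background names concerns new infestation in contacts, and a favourable household result could be taken to fill it when the result came wholly from curing existing cases. Second, with about 35 households, the arms may differ by chance in how many cases they start with. The trial collects what it needs to allow for this but does not say that it will.

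**Working it through.** **The plan's own figure.** The only sample size given is for the primary endpoint: 35 affected subjects per group for 70% versus 95% cure, 80% power, alpha 0.05. A two-sided comparison of two proportions with pooled variance and no continuity correction gives 36 per group, and 35 per group gives 79.9% power. The figure reproduces, and nothing below alters it. No sample size is given for the household endpoint.

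**Inputs from the documents.** On average two affected members present per household (the index case plus one). There are at least 35 households, so 17–18 per arm if allocation is equal, which is assumed.

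**Inputs assumed, because the documents do not give them.** Household size H = 5. There are u affected members at home who do not present. The cure rate c among those who use treatment is the same in both arms. Untreated cases are not cured. There are no new infestations in either arm.

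**Expected cases per household at week 4 with zero prevention**

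- Individual arm: 2(1 − c) + u
- Household arm: 2(1 − c) + u(1 − c)
- Difference: u × c cases, or u × c / H as a proportion of members

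| u | c = 80% | c = 95% |
|---|---|---|
| 0 | 0 points | 0 points |
| 0.5 | 0.40/5 = 8 points | 0.475/5 = 9.5 points |
| 1 | 0.80/5 = 16 points | 0.95/5 = 19 points |

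Worked example at u = 1, c = 90%: individual (0.2 + 1)/5 = 24%, household 0.3/5 = 6%, a difference of 18 points. If only a fraction a of the affected members at home use the treatment, the difference is a × u × c / H. At a = 0.5 (assumed) the bottom row halves to 8–9.5 points.

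**Simulation.** With 18 versus 17 households of 6, Poisson-distributed u, a 10% new-case risk in both arms, Welch's t-test and 3,000 runs per setting:

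| Mean u | All cases, c = 70% | All cases, c = 95% |
|---|---|---|
| 0 | about 5% | about 5% |
| 0.5 | about 16% | about 41% |
| 1 | about 45% | about 88% |

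The entries are the chance of p < 0.05. When only members free of scabies at baseline were counted, the chance stayed near 5% in every setting. The simulation assumes that baseline status is known without error.

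**Chance imbalance.** If the baseline proportion affected has a between-household SD of 0.15–0.25 (assumed), the 95% range of the arm difference at baseline is ±1.96 × SD × √(2/17.5), which is ±9.9 to ±16.6 points. Not all of that survives to week 4. Suppose that all the variation comes from cases at home and that c = 90%. It then carries over in full in the individual arm and by a factor of 0.1 in the household arm. The range becomes ±1.96 × SD × √((1 + 0.01)/17.5), or ±7.1 points at SD 0.15 and ±11.8 at SD 0.25. It is smaller if part of the variation comes from members who present, because they are treated in both arms.

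**The case against.** The strongest reply is that the endpoint is right for its objective. The secondary objective is worded as the proportion affected at week 4, and the Research question section sets out to assess the practice of recommending household treatment. Treating affected members who stayed at home is part of that practice, and allocation is randomised. The resulting difference is therefore a true effect of the strategy. This stands. A reader might infer from the simulation that the endpoint is biased or gives false positives. It does not: for the stated objective, those percentages are power to detect a real strategy effect. They would be false positives only for a claim of prevention, and no section says that the result will be read that way. The prevention aim that the protocol does state is avoiding reinfestation of the index case, which the primary endpoint addresses.

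Three other strong readings also fail:

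- *Old and new cases cannot be told apart at all.* Members who present are examined at baseline, and a household-level count exists before and after treatment. What is missing is member-level status for those who did not present, and a stated use of the count.
- *Baseline imbalance passes straight into week 4, at 10–17 points.* Cure removes much of it. The ceiling is about 7–12 points, and it is random error rather than bias.
- *Counting new cases would settle the prevention question.* Symptoms can take up to 6 weeks and follow-up is at 4, so some apparent new cases were already infested at baseline. Only the household arm would have treated them.

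It is also fair to say that the size rests on assumed inputs and vanishes at u = 0. Use of the treatment is unsupervised, so real differences may be smaller. The treatment section taken alone is less explicit than the Research question section about affected members at home; if they were treated in both arms, the mechanism would disappear.

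**Conclusion.** The point holds in a limited form. The all-cases household proportion is a sound strategy-level endpoint. It does not use baseline information that the trial already collects, and it cannot support a statement about preventing new infestation in contacts. With zero prevention, the expected arm difference is u × c cases per household: 0 points at u = 0, 8–9.5 at u = 0.5 and 16–19 at u = 1, for a household of 5 with c of 80–95%, and less if uptake is incomplete. Chance imbalance at baseline could add random error of at most about ±7–12 points under the assumptions above. All these sizes depend on inputs that the documents do not give, and on the Research question section's account of who is treated. The point concerns a secondary endpoint only.

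**What to change.** 1. Reconcile the Research question and Study treatment sections on whether affected members at home in the individual arm receive treatment.
2. Adjust the week-4 household proportion for the baseline proportion of probable cases. The count and household size are already collected, so this costs one line in the analysis plan. It addresses the chance imbalance, for which 7–12 points is a ceiling.
3. Take the responsible person's baseline report before the arm is revealed, in both arms, as a yes/no for each household member. Timing matters because, under Ethical Considerations, only the household arm is told of the wider treatment after randomisation. As a descriptive supporting analysis, report new cases among members unaffected at baseline separately from persistence among those affected.
4. Keep the all-cases proportion as the strategy-level result, and state that it is not to be interpreted as prevention of new infestation.

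The cost is a short household list in place of a count, one adjusted analysis and one split table, with no added visits or participants. The responsible person must be asked before disclosure. There are three limits: baseline status is proxy-reported, the split will be imprecise with about 35 households, and the incubation period means that it separates the two effects only in part.

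### Whole households are randomised, but the sample size counts 35 independent people per group, so the stated 80% power makes no allowance for clustering and the primary analysis unit is left open

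*Combined protocol and SAP*

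**What the plan says.** The Sample size section starts from "Estimating a cure rate of 70% and 95% for individual vs. family treatment respectively" and concludes that "we calculated a sample size of 35 affected subjects per group to provide a power of 80% with an alpha of 0,05". It then supposes that each index case brings one further affected household member on average, and on that basis says "we will aim to include at least 35 different households".

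Under Study treatment and follow up, the index case is randomised and "subjects of the respective household will follow the randomization outcome of the index case". The household is therefore the randomised unit.

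The unit of analysis is described in more than one way. The Research question section asks "if it provides a benefit for the index case by preventing reinfestation". The primary objective reads "To compare the effectiveness of individual vs household treatment for persons affected by scabies". The primary endpoint is clinical cure at 4 weeks, with no statement of whose cure is counted. The document has no statistical analysis section and gives no ICC, design effect, primary test or model.

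**The concern.** The planned 70 subjects are 35 households times 2, so the second affected person in each household is counted as a full independent observation. The trial's own rationale makes that doubtful. It supposes that untreated household members reinfest treated ones, and members of one household share that source. Treatment is also unsupervised, so they may share adherence as well. Some positive correlation of cure within a household is therefore plausible, although its size is unknown.

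Three analyses remain open, and each has a different consequence:

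- **All affected subjects, household accounted for:** valid, but with less power than stated once correlation is more than slight.
- **All affected subjects, treated as independent:** this is what the sample size assumes, and it rejects too often when there is correlation.
- **Index cases only:** the error rate holds, but about half the planned observations are lost.

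Because nothing is prespecified, the choice could be made after the data are seen.

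**Working it through.** **Inputs from the protocol.** Cure 70% vs 95%; 35 affected subjects per group; power 80%; alpha 0.05; mean of 2 affected subjects per household; at least 35 households.

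**Assumptions.** Two-sided test and 1:1 allocation (neither is stated), so 17 vs 18 households at the minimum target. The ICC is not in the document; 0.1, 0.3 and 0.5 are shown, with 0.05 as a low case.

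**1. The plan's figure.** Pooled-variance formula, mean cure rate 0.825:

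n = [1.960 × √(2 × 0.825 × 0.175) + 0.842 × √(0.70 × 0.30 + 0.95 × 0.05)]² / 0.25² = (1.053 + 0.427)² / 0.0625 ≈ 35.06 per group.

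Power at 35 = Φ[(0.25 × √35 − 1.053) / 0.507] = Φ(0.839) = 79.9%. The stated number is thus the independent-subjects formula with a design effect of 1. A one-sided test would give 28, and a continuity correction 43.

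**2. Power with pairs.** Design effect = 1 + (2 − 1) × ICC; effective n = 35 / (1 + ICC), put into the same power formula. The last two columns are simulated (beta-binomial, 17 vs 18 households) for a size-weighted household comparison with cluster-robust variance and t on households − 2 df. Household sizes are either fixed at 2 or drawn as 1 + Poisson(1).

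| ICC | Effective n per arm | Formula power | Simulated, pairs | Simulated, variable sizes |
|---|---|---|---|---|
| 0 | 35.0 | 79.9% | 81.5% | 81.8% |
| 0.05 | 33.3 | 77.9% | 80.8% | 79.9% |
| 0.1 | 31.8 | 75.9% | 78.5% | 76.3% |
| 0.3 | 26.9 | 68.5% | 71.0% | 67.9% |
| 0.5 | 23.3 | 62.0% | 63.9% | 60.8% |

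The simulated test keeps its alpha at 4.7–5.7%.

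**3. Type I error if household is ignored.** For pairs, the approximation is 2 × [1 − Φ(1.960 / √(1 + ICC))] = 6.2%, 8.6% and 11.0% at ICC 0.1, 0.3 and 0.5. Simulation with a common cure rate of 82.5% gives:

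| Test | Sizes | ICC 0.1 | ICC 0.3 | ICC 0.5 |
|---|---|---|---|---|
| Chi-square | pairs | 5.7% | 8.6% | 10.8% |
| Chi-square | variable | 7.1% | 10.2% | 13.6% |
| Fisher | pairs | 4.2% | 6.3% | 8.2% |
| Fisher | variable | 4.6% | 7.6% | 10.3% |

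**4. Index cases only.** With 17 vs 18 people, the normal approximation gives 48.7–50.1% power, depending on which arm has 18. Exact calculation gives 50.9–54.8% for chi-square and 39.3–48.8% for Fisher. No ICC is involved.

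**5. Households for 80%.** Per arm, ⌈35.06 × (1 + ICC) / 2⌉ = 20, 23 and 27, so 40, 46 and 54 in total at ICC 0.1, 0.3 and 0.5. Simulated power of the weighted test at these totals with variable sizes is 83.1%, 80.2% and 80.0%. For index cases only, 35–36 per arm are needed, so 70–72 in total.

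**The case against.** The best reply is that the damage may be small. The document gives no ICC, so nothing in it favours 0.3 or 0.5 over 0.05, and with pairs the design effect cannot exceed 2. At ICC 0.05 the simulated household test still has 79.9–80.8% power. At 0.1 it has 76.3–78.5%. The planning formula starts at 79.9%, so it falls below 80% at once for any positive ICC. This stands: the shortfall is negligible for a very small ICC, and its size is uncertain. It does not rescue the plan, which neither states nor justifies a small ICC.

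It can also be said that inflated alpha is a risk and not a planned error, since no chi-square test is named, and Fisher's test shows no inflation at ICC 0.1. That is fair, but Fisher's test does exceed 5% at ICC 0.3 and 0.5, and no test is prespecified.

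The index-only reading rests on one sentence of rationale, while the primary objective and the sample size both point to all affected persons. That supports choosing all affected subjects, but the endpoint itself still names no unit.

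Finally, 35 households is a minimum, so 17–18 per arm is a floor that assumes equal allocation. Nothing commits the trial to more, and the 80% claim is attached to 35 subjects per group.

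**Conclusion.** The concern holds. The arithmetic behind 35 per group is sound, but it belongs to a trial that randomises individuals, and this one randomises households. By the planning formula, 80% is delivered only if all affected subjects are analysed and cure is uncorrelated within households.

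Confidence is high that no allowance for clustering was made and that the unit is not fixed. The size of the loss depends on an ICC the document does not give: a few points at 0.05–0.1, and roughly 11 to 18 points by the formula at 0.3–0.5 (79.9 − 68.5 = 11.4; 79.9 − 62.0 = 17.9). The drop to about 50% applies only if index cases alone are analysed. The missing household-adjusted analysis must be corrected whatever the ICC, because it determines whether the primary test is valid.

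**What to change.** 1. State the primary analysis unit: all affected subjects enrolled, as the sample size implies. If the sponsor prefers index cases only, the target has to be about 70–72 households.
2. Specify an analysis with household as the cluster: GEE or mixed logistic regression with a small-sample correction, or household cure proportions weighted by the number of affected members. An unweighted comparison of household proportions is inefficient here: with variable sizes its power is 74.6% at ICC 0, against 81.8% weighted.
3. Restate power with the ICC assumption shown: roughly 62–76% for ICC 0.1–0.5 by the formula for pairs, and about 61–76% in simulation with variable household sizes. State the sidedness and allocation ratio as well.
4. Optionally, to keep 80%, raise the target to about 40–54 households over the same ICC range. This is compatible with a target already worded as a minimum.

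Items 1 to 3 cost protocol wording and a household-adjusted model. They need no extra patients, but the stated power becomes less favourable. Item 4 costs about 5 to 19 more households (40 − 35 to 54 − 35).

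### Severity is graded for each case, but the plan makes no use of it in the primary cure comparison; one pre-specified severity score would be a cheap, modest gain

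*Combined protocol and SAP*

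**What the plan says.** The four-level grade appears under Scabies Diagnosis and Data Collection: "A severity scale will be used classifying the cases into mild, moderate, severe and crusted according to the number of lesions counted". The only stated use for clinical description is a descriptive secondary objective (Study Objectives).

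The primary endpoint is binary: "The primary efficacy outcome will be clinical cure after 4 weeks". Study treatment and follow up defines cure relative to the starting lesions: they must have improved and none may be new. The same section says that index cases are randomised in REDCap and that "subjects of the respective household will follow the randomization outcome of the index case". It mentions no stratification.

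The Sample size section opens with its assumed rates: "Estimating a cure rate of 70% and 95% for individual vs. family treatment respectively". The result is reported in these words: "we calculated a sample size of 35 affected subjects per group". Power is set at 80% and alpha at 0.05. The target number of households, at least 35 in total, follows from the expectation that "on average one additional household member affected will present at the medical research center alongside an index case".

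There is no statistical analysis section. The document names no test, model, covariate or analysis set for the primary comparison, and no method for correlation within households.

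**The concern.** Cure is judged against the lesions a patient started with, so starting lesion burden is a natural candidate predictor of cure, and the trial already plans to grade it. With few randomised units, the arms can differ in severity by chance. If severity predicts cure, an unadjusted difference then moves up or down with that imbalance, and its variance is larger than it need be. If the covariate is not named in advance, any later adjustment is also open to the criticism that it was chosen after the data were seen.

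**Working it through.** **1. The plan's own figure.** Inputs from Sample size: 70% and 95% cure, 80% power, alpha 0.05 (two-sided assumed, since it reproduces the figure). The pooled-variance formula, with mean proportion 0.825, gives

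n = [1.960·√(2·0.825·0.175) + 0.842·√(0.70·0.30 + 0.95·0.05)]² / 0.25² = 35.06 per arm.

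Power at 35 per arm is 79.9%. The stated 35 is therefore reproduced, with subjects treated as independent and no covariate.

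**2. Randomised units.** The plan expects 2 affected subjects per household and at least 35 households. At 1:1 (inferred from the equal group sizes), 35/2 = 17.5, so 17 or 18 households per arm.

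**3. Chance imbalance.** Assume half the cases are moderate or worse, with 2 cases per household and within-household severity correlation ρ. The SD of the between-arm difference in that share is about √(2·0.25/35)·√(1+ρ).

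| ρ | SD | Chance of a gap of 20 points or more (simulated) |
|---|---|---|
| 0 | 0.12 | 9% |
| 0.3 | 0.14 | 14% |
| 1 | 0.17 | 23% |

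**4. Average gain from adjustment.** Simulated trials at 70% vs 95% cure, 4000 per setting. Each was analysed by least squares on arm, with and without a 0-3 severity score, using household-clustered standard errors and a t reference. The severity mix (mild/moderate/severe/crusted) and the odds ratio for non-cure per step are assumptions.

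- A: 35 households of 2, mix 50/30/17/3%, some sharing of severity within households, no household effect on cure.
- B: as A, with a household SD of 1 on the logit scale.
- C: 35 households of 2, mix 40/35/20/5%, severity independent within households, household SD 1.
- D: 36 households with mean size 2, mix 40/35/20/5%, household SD 1.

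| Setting | Odds ratio per step | Variance ratio, adjusted/unadjusted | Power, unadjusted to adjusted |
|---|---|---|---|
| A | 1 | 1.02 | 82.8% to 82.3% |
| A | 2 | 0.96 | 82.2% to 84.2% |
| A | 3 | 0.87 | 81.6% to 86.0% |
| B | 2 | 0.97 | 78.3% to 80.0% |
| B | 3 | 0.91 | 79.1% to 82.4% |
| C | 3 | 0.93 | 79.1% to 82.0% |
| D | 2 | – | 79.1% to 79.8% |
| D | 3 | (0.0878/0.0906)² = 0.94 | 79.3% to 81.8% |

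At an odds ratio of 2 the gain is close to simulation error and should be read as a few percent at most. If only two severity levels are occupied, in equal shares, the gain shrinks: the variance ratio is 0.98 at an odds ratio of 3. Type I error lay between 4.6% and 6.3% throughout, adjusted or not.

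**5. The single trial.** In setting C, the household arm started worse by 0.3 or more mean severity steps in about 8% of trials, and better by that much in another 8%. At an odds ratio of 3, the true 25-point difference averaged 20.8 points unadjusted in the first group and 30.5 in the second. The adjusted averages were 25.0 and 25.5. Power in the unfavourable group was 64% unadjusted and 80% adjusted.

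**6. Events.** Expected non-cures are 35·0.30 + 35·0.05 = 10.5 + 1.75, about 12. The chance of none in the household arm is 0.95³⁵ = 17%.

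**7. Scale against clustering.** With 2 per household, effective n per arm is 35/(1+ICC). Power falls from 80% to 76%, 72%, 68% and 62% at ICC 0.1, 0.2, 0.3 and 0.5, a loss of 4 to 18 points.

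**The case against.** The strongest reply is that severity may not predict cure. The endpoint is change from each patient's own start, which does not show that heavier disease fails more often. The mechanism under test is reinfestation, which points at least as much to household size, also collected. The documents give no association, and at an odds ratio of 2 the gain is slight. This stands: the size of the gain is an assumption and there may be none.

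A second reply is that about 12 non-cures are too few for covariates. That is right for three indicator terms in a logistic model, where sparse cells or separation are likely. It also counts against a binomial identity-link fit, which may not converge with cure near 95%. It does not rule out one ordered score in a least-squares model.

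Three stronger readings are tempting, and the documents support none of them:

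- A reader might infer that the plan has chosen a crude comparison. No analysis is stated at all, so severity is neither adopted nor ruled out.
- A reader might infer that chance imbalance invalidates the unadjusted test. Under randomisation it does not, and the simulated type I error stays near 5%.
- A reader might call the precision free. It costs a degree of freedom, and some power if severity is not prognostic.

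**Conclusion.** The point holds as a modest, low-cost improvement. The grade is planned, no use of it in the primary comparison is planned, and with 17 to 18 households per arm a notable imbalance is plausible. Expected gains are about 3-4% less variance at an odds ratio of 2 per step and about 7-13% at 3 (6% in the variant with varying household size), or about 1-2 and 2.5-4 points of power. If severity is not prognostic, variance rises by about 1-2% and up to 1 point of power is lost. These figures rest on assumed severity mixes, associations and household effects. The stronger argument is protection of the one result that will be seen when the draw is unlucky. The protocol only implies, by placing the grade under diagnosis, that grading precedes allocation. Accounting for household clustering matters more and should be settled first.

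**What to change.** Add to the protocol, as part of the primary analysis text:

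- Severity is graded and recorded before allocation is known.
- The primary analysis is a linear (least-squares) regression of cure on arm plus severity as one 0-3 score, giving a risk difference. Standard errors are clustered on household, with a small-sample correction: a t reference on households minus 3 degrees of freedom (35 − 3 = 32).
- The unadjusted clustered difference is reported beside it (35 − 2 = 33 degrees of freedom).
- A binomial identity-link fit is not used.

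The cost is a few lines of text and one degree of freedom. The grade is already planned; the only operational demand is that it be fixed before randomisation.
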